7.1.2 Treatment period

The subject will attend ambulatory visits on Days 1, 2, 5, 7, 14, 28, 56, and 84 (end of study).

The following procedures will take place during the treatment period:

- SUBJECT SELECTION (**Day 1 visit**): Inclusion criteria no. [7](#) and exclusion criteria no. [1](#), [2](#), [12](#), [14](#), [18](#), [19](#), [27](#), and [32](#) will be re-checked as requested in [Sections 4.2](#) and [4.3](#). Subjects not fulfilling the mentioned criteria will be screen failed.
- RANDOMISATION (**Day 1 visit**): Subjects will be randomised to receive a single IV dose of CHF10067 or placebo.
- DOSING (**Day 1 visit**): Subjects will be administered a single IV dose of CHF10067 or placebo.
- PHYSICAL EXAMINATION (**Day 1, 2, 5, and 7 visits**): A full physical examination will be performed according to [Section 7.2.10](#) and any new revealed clinically significant abnormality since the last visit will be recorded as an AE.
- ABBREVIATED PHYSICAL EXAMINATION (**Day 14, 28, 56, and 84 visits**): A symptom-directed physical examination will be performed according to [Section 7.2.10](#) and any new revealed clinically significant abnormality since the last visit will be recorded as an AE.
- ADVERSE EVENTS RECORDING (**all visits**): Any new AE/SAE occurred since the last visit will be checked and recorded in the eCRF. The status of ongoing AEs will be checked and updated in the eCRF when applicable. Moreover, during this period in case of any new clinically significant abnormality revealed during the examination or procedures, it will be recorded as an AE.
- STUDY RESTRICTIONS (**all visits**): Study restrictions criteria will be checked according to [section 7.1.4](#).
- CONCOMITANT MEDICATIONS CHECK (**all visits**): Concomitant medications taken by the subject since the last visit will be checked and recorded in the eCRF.
- BLOOD TESTING: Blood sample collection for safety evaluations (clinical chemistry, haematology, fasting glucose [**Day 1 pre-dose, 2, 7, 14, 28, 56, and 84 visits**], immunogenicity [**Day 1 pre-dose, 14, 28, 56, and 84 visits**], and markers for evaluation of immediate hypersensitivity reactions [**Day 1 visit**]) according to [Sections 7.2.2.1](#),

Clinical Study Code No.: CLI-10067AA1-01	Version No.: 6.0
EUDRACT No.: 2022-001079-15	Date: 06 July 2023

7.2.2.4 and **7.2.2.5**. Subjects have to be in fasting condition from at least 10 hours before clinical chemistry and fasting glucose samples are collected.

- **URINE TESTING:** Urine samples for pregnancy testing (females of childbearing potential [**Day 1, 28, 56, and 84 visits**]) will occur according to [Section 7.2.6](#)
- **PHARMACOKINETIC INVESTIGATION (all visits):** Collection of blood for PK assessment according to [Section 7.2.1](#).
- **VITAL SIGNS (all visits):** Measurement of systolic and diastolic blood pressure, pulse rate, respiratory rate, and body temperature according to [Section 7.2.8](#).
- **LOCAL ECG (Day 1, 2, 7, 28, and 84 visits):** Single 12-lead ECG will be used to measure heart rate, PR, QRS, and QTcF according to [Section 7.2.9](#).
- **PULMONARY ASSESSMENTS:** Oxygen saturation (**all visits**), Spirometry (**Day 7, 28, 56, and 84 visits**); FEV₁, FEV₁ % of predicted normal and lower limit of normal value, FVC, FVC% of predicted normal and lower limit of normal value, FEV₁/FVC, and diffusing capacity (**Day 28, 56, and 84 visits**); D_{LCO}(unadjusted), D_{LCO} % predicted, D_{LCO} corrected for haemoglobin, D_{LCO} corrected for haemoglobin % predicted, KCO, and VA) will be measured according to [Section 7.2.7](#).
- **TG-2 ASSESSMENT (Day 1, 14, 28, 56, and 84 visits):** Transglutaminase 2 levels in plasma will be measured according to [Section 7.2.3](#).
- **NASO-ABSORPTION SAMPLES (Day 1 and Day 14 visits):** Two mucosal samples (one from each nostril) will be taken at each timepoint according to [Section 7.2.5](#).
- **SERUM PROTEOMIC SAMPLE (Day 1 and Day 14 visits):** A blood sample for serum proteomic analysis will be taken at each timepoint according to [Section 7.2.4](#).
- **PLASMA PROTEOMIC SAMPLE (Day 1 visit):** A blood sample for plasma proteomic analysis will be taken at each timepoint according to [Section 7.2.4](#).
- **OPTIONAL TRANSCRIPTOMIC SAMPLES (Day 1 and Day 14 visits):** Two blood samples for possible whole blood transcriptomic analysis will be taken at each timepoint according to [Section 7.2.11](#).

7.1.3 Early termination

The following procedures will take place at the early termination visit in case of subject discontinuation/withdrawal:

- **PHYSICAL EXAMINATION:** A full physical examination will be performed according to [Section 7.2.10](#) and any new revealed clinically significant abnormality since the last visit will be recorded as an AE.
- **ADVERSE EVENTS RECORDING:** Any new AE/SAE occurred since the last visit will be checked and recorded in the eCRF. The status of ongoing AEs will be checked and updated in the eCRF when applicable. Moreover, in case of any new clinically significant abnormality revealed during the examination or procedures, it will be recorded as an AE.
- **CONCOMITANT MEDICATIONS CHECK:** Concomitant medications taken by the subject since the last visit will be checked and recorded in the eCRF.

Clinical Study Code No.: CLI-10067AA1-01	Version No.: 6.0
EUDRACT No.: 2022-001079-15	Date: 06 July 2023

- **BLOOD TESTING:** Blood sample collection for safety evaluations (clinical chemistry, haematology, fasting glucose) and immunogenicity according to [Sections 7.2.2.1](#) and [7.2.2.4](#).
- **VITAL SIGNS:** Measurement of systolic and diastolic blood pressure, pulse rate, respiratory rate, and body temperature according to [Section 7.2.8](#).
- **LOCAL ECG:** Single 12-lead ECG will be used to measure heart rate, PR, QRS, and QTcF according to [Section 7.2.9](#).
- **PULMONARY ASSESSMENTS:** Oxygen saturation, Spirometry (FEV₁, FEV₁ % of predicted normal and lower limit of normal value, FVC, FVC % of predicted normal and lower limit of normal value, and FEV₁/FVC), and diffusing capacity (D_{LCO} [unadjusted], D_{LCO} % predicted, D_{LCO} corrected for haemoglobin, D_{LCO} corrected for haemoglobin % predicted, KCO, and VA) will be measured according to [Section 7.2.7](#).

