7. STUDY PLAN

7.1 Study Schedule – All Cohorts

	Screening (Days -28 to -3)	Treatment Period					Early Termination
		Day 1	Day 2	Days 5 and 7 (\pm 1 day)	Days 14, 28, and 56 (\pm 2 days)	Day 84 (\pm 2 days)	
Informed consent	X						
Randomisation		X					
Ambulatory visit	X	X	X	X	X	X	X
Treatment Intake							
CHF10067 or placebo administration ^a		X					
Subject Health Evaluation							
In/Ex criteria	X	X ^b					
Medical history	X						
Demographic data	X						
Height and weight	X						
Alcohol breath test	X						
Physical examination	X	X	X	X			X
Abbreviated physical examination					X	X	
Adverse events recording	X	X	X	X	X	X	X
Restrictions	X	X	X	X	X	X	
Concomitant medication	X	X	X	X	X	X	X
Safety Assessment in Blood							
Fasting clinical chemistry	X	X (pre-dose)	X	X ^h	X	X	X
Haematology	X	X (pre-dose)	X	X ^h	X	X	X
Fasting glucose	X	X (pre-dose)	X	X ^h	X	X	X
FSH (post-menopausal female subjects) and/or pregnancy test (females of childbearing potential)	X						
Serology	X						
Markers for evaluation of immediate hypersensitivity reactions		X ^f					
ADA and nAb (in case of positive ADA)		X (pre-dose)			X	X	X
Other Assessments							
TG2 levels		X (pre-dose)			X	X	
Naso-absorption samples		X (pre-dose)			X ⁱ		
Proteomic sample (serum)		X (pre-dose)			X ⁱ		
Proteomic sample (plasma)		X (pre-dose)					
Optional transcriptomic samples		X (pre-dose)			X ⁱ		
Assessments in Urine							
Urinalysis	X						
Drug screen	X						

Clinical Study Code No.: CLI-10067AA1-01	Version No.: 6.0
EUDRACT No.: 2022-001079-15	Date: 06 July 2023

	Screening (Days -28 to -3)	Treatment Period					Early Termination
		Day 1	Day 2	Days 5 and 7 (\pm 1 day)	Days 14, 28, and 56 (\pm 2 days)	Day 84 (\pm 2 days)	
Cotinine	X						
Pregnancy test (females of childbearing potential)		X			X ^j	X	
Pharmacokinetic in Blood^c							
CHF10067		X	X	X	X	X	
Safety Cardiac Assessments							
Vital signs ^d	X	X	X	X	X	X	X
Local 12-lead ECG ^e	X	X	X	X	X	X	X
Safety Pulmonary Assessments							
Oxygen saturation ^g	X	X	X	X	X	X	X
Spirometry	X			X ^k	X ^k	X	X
Diffusing capacity	X				X ^l	X	X

Abbreviations: ADA = anti-drug antibody; ECG = electrocardiogram; FSH = follicle-stimulating hormone; In/Ex = inclusion/exclusion; nAb = neutralising antibody; TG2 = transglutaminase 2.

Footnotes for Evaluation Schedule:

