^a Special attention will be given to immediate hypersensitivity reactions and monitoring up to 8 hours post-dose is required. If the subject has no symptoms, he/she can be discharged. If the subject has symptoms, he/she may remain overnight. An overnight stay is also permitted for logistical reasons and/or site's/subject's preference.

^b Specific In/Ex criteria will also be checked pre-dose on Day 1 according to study schedule and In/Ex criteria.

^c Pharmacokinetic blood samples for serum CHF10067 will be collected at the following timepoints: pre-dose (within 75 minutes from start of infusion), at the end of infusion, and 2, 4, 8, and 20 hours after the end of the infusion and 5, 7, 14, 28, 56 and 84 days post-dose.

^d Vital signs (blood pressure, pulse rate, respiratory rate, body temperature): systolic and diastolic blood pressure will be evaluated in duplicate after 5 minutes in supine position. Vital signs will be measured at screening and at the following timepoints: pre-dose, every 15 minutes during the infusion (e.g., 15, 30, 45, 60, 75, 90, 105, etc.), at the end of the infusion and 30 min, 1, 2, 3, 4, 6, 8, and 20 hours after the end of the infusion and 5, 7, 14, 28, 56, and 84 days post-dose.

^e Local 12-lead ECG: a triplicate ECG will be performed to assess eligibility and a single ECG will be evaluated at all other timepoints. Electrocardiograms will be measured at screening and at the following timepoints: pre-dose on Day 1, and Days 2, 7, 28, and 84.

^f Markers for evaluation of immediate hypersensitivity reactions: pre-dose for all subjects. If required (based on subject experiencing symptoms of immediate hypersensitivity reactions), blood samples will be collected at 1 and 2 hours after the onset of the event.

^g Oxygen saturation: will be measured at screening and continuous monitoring will occur from pre-dose to 10 hours post-dose at the following timepoints: pre-dose, every 15 minutes during the infusion (e.g., 15, 30, 45, 60, 75, 90, 105, etc.), at the end of the infusion and 30 min, 1, 2, 3, 4, 6, 8, hours after the end of infusion. Oxygen saturation will also be measured at 20 hours after the end of infusion, and 5, 7, 14, 28, 56 and 84 days post-dose.

^h Clinical laboratory evaluations will be conducted on Day 7 only.

ⁱ Sample(s) will be collected on Day 14 only.

^j Pregnancy test conducted on Days 28 and 56.

^k Spirometry conducted on Days 7, 28, and 56 only.

^l Diffusing capacity conducted on Days 28 and 56 only.

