7.2.2.4 Immunogenicity

The following blood samples will be collected pre-dose and Days 14, 28, 56, and 84:

- 5 mL of blood for immunogenicity assessments (serum non-isotype ADAs) and nAb (in case of ADA positive result).

The analytical procedures will be described in a separate analytical protocol. Validation data and details of the analytical procedures will be gathered in an analytical report that will be included in the Clinical Study Report. The processing, storage and shipment of samples are detailed in the Laboratory Manual document.

Antibodies to CHF10067 will be evaluated in blood samples collected from all subjects according to the study schedule (Section 7.1). Additionally, samples should be collected at the early termination visit from subjects who discontinued study drug or were withdrawn from the study. These samples will be tested by the Sponsor or Sponsor's designee.

Clinical Study Code No.: CLI-10067AA1-01	Version No.: 6.0
EUDRACT No.: 2022-001079-15	Date: 06 July 2023

Samples will be screened for antibodies binding to CHF10067, and the titer of confirmed positive samples will be reported. Other analyses may be performed to further characterise the immunogenicity of CHF10067. In particular, positive ADA samples will be also evaluated for the presence of IgE CHF10067, to clarify the relationships between this ADA subtype and the presence of adverse reactions.

The detection and characterisation of antibodies to CHF10067 will be performed using a validated assay method by or under the supervision of the Sponsor. All samples collected for detection of antibodies to study drug will also be evaluated for CHF10067 concentration, to enable interpretation of the antibody data. Antibodies may be further characterised and/or evaluated for their ability to neutralise the activity of the study drug. Samples may be stored for a maximum of 20 years (or according to local regulations) following the last subject's final visit for the study at a facility selected by the Sponsor to enable further analysis of immune responses to CHF10067.

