7.2.6 Urine collection for safety evaluation

The following urine sample will be collected at screening:

Clinical Study Code No.: CLI-10067AA1-01	Version No.: 6.0
EUDRACT No.: 2022-001079-15	Date: 06 July 2023

- Urine sample for urinalysis – quantitative (proteins) and urinalysis – qualitative (ketones, microscopic examination of the sediment)
- Urine sample for drug test (cannabinoids, opiates, cocaine, benzodiazepines, amphetamines, barbiturates)
- Urine sample for cotinine test.

The following urine samples will be collected on the Day 1, 28, 56, and 84 visit:

- Urine sample for pregnancy test.

Urine collection and sample preparation will be performed according to procedures provided by the local laboratory which will be in charge to transmit the results to the Investigator for entry in the eCRF.

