7.2.7 Pulmonary assessments for safety evaluation

7.2.7.1 Spirometry

Spirometry will be assessed at the following timepoints: screening, 7, 28, 56, and 84 days post-dose and in case of early termination visit.

Spirometry will be assessed centrally. The specific procedures for centralized spirometry will be provided to the Investigator by the centralized spirometry company. The same brand and model of spirometer will be provided by the centralised spirometry company for all measurements and adjusted for the ATS/ERS standards [20]. Lung function measurements will be done with subjects sitting with the nose clipped after at least 10 minutes rest. Values will be corrected for body temperature and pressure (saturated) conditions.

The following parameters (but not limited to) will be recorded: FEV₁, FVC, FEV₁% of predicted normal and lower limit of normal value, FVC % of predicted normal and lower limit of normal value, and FEV₁/FVC ratio.

Predicted values of FEV₁ will be calculated according to formulas reported by Quanjer et al. [21].

For FEV₁ and FVC, the highest value from 3 technically satisfactory attempts will be recorded in the eCRF (irrespective of the curve they come from). The chosen value should not exceed the next one by more than 150 mL. If the difference is larger, up to 8 measurements will be made and the largest value be reported. In order to be considered as technically satisfactory attempts, measurements should be free from cough and false-start and meet all the ERS/ATS criteria. The FEV₁/FVC should be taken from the highest FEV₁ and FVC values (even if not coming from the same curve). The acceptability criteria for spirometry assessment will be further specified in separate documents.

For inclusion criterion no. 8 if the criterion is not met at screening, the subject may repeat the tests. If at that time the values fall within the ranges specified, the subject can be included in the study, otherwise the subject will be discharged and recorded as screening failure.

Clinical Study Code No.: CLI-10067AA1-01	Version No.: 6.0
EUDRACT No.: 2022-001079-15	Date: 06 July 2023

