3.2 CLINICAL LABORATORY EVALUATION

3.2.1 Available data

Per protocol, the following safety laboratory parameters are expected to be collected at Screening, at Day 1 pre-dose, at Day 2, 7, 14, 28, 56 and 84:

- Biochemistry: creatinine, urea, aspartate aminotransferase, alanine aminotransferase, gamma-glutamyl transpeptidase, total bilirubin, alkaline phosphatase, sodium, potassium, chlorine, and fasting glucose.
- Haematology: red blood cells count, white blood cells count and differential (neutrophils, eosinophils, lymphocytes, monocytes, basophils; % and values), total haemoglobin, haematocrit, and platelets count.
- Urinalysis (at Screening only): quantitative (proteins) and urinalysis – qualitative (ketones, microscopic examination of the sediment), will only be listed.
- Serum and urine pregnancy test and FSH (at Screening, Day 1, Day 28, Day 56, and Day 84 only), will only be listed.

Normal ranges are available as provided by the laboratory.

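### The Early Termination visit repeats the other Day 84 safety assessments but not the urine pregnancy test, so a woman of childbearing potential who leaves before Day 28 has no scheduled post-dose test

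*Protocol*

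**What the plan says.** Protocol Section 4.4 calls for an Early Termination visit, devoted to safety assessments, for any subject who leaves and has not withdrawn consent. Section 7.1.3 lists its content:

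- a full physical examination, adverse event recording and a concomitant medication check;
- blood tests, worded as "Blood sample collection for safety evaluations (clinical chemistry, haematology, fasting glucose) and immunogenicity according to" Sections 7.2.2.1 and 7.2.2.4;
- vital signs, ECG, oxygen saturation, spirometry and diffusing capacity.

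It has no urine item.

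The days of the urine pregnancy test are set in three places in the protocol:

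- Section 7.2.6: "The following urine samples will be collected on the Day 1, 28, 56, and 84 visit".
- Section 7.1.2, under urine testing: Days 1, 28, 56 and 84.
- The Section 7.1 schedule: marks at Day 1, at the grouped Day 14/28/56 column (with the footnote "Pregnancy test conducted on Days 28 and 56") and at Day 84. The Early Termination cell is empty.

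The SAP 10.2 copy of the schedule shows the same pattern. Exclusion criterion 32 puts the Day 1 urine test before randomisation, so it is a pre-dose test.

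Other investigation sections do provide for leavers. Section 7.2.2.4 says "samples should be collected at the early termination visit from subjects who discontinued study drug or were withdrawn from the study", and Section 7.2.7.1 schedules spirometry at "screening, 7, 28, 56, and 84 days post-dose and in case of early termination visit".

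**The concern.** A completer is tested for pregnancy at the end of participation. A leaver who received the same single Day 1 infusion is not, and neither document gives a reason for the difference.

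Early exit is foreseen. Section 4.4 plans replacements so that eight evaluable subjects per dose level complete Day 14, which falls before the first post-dose pregnancy test. Section 10.11 requires a pregnancy found after dosing to be reported within 24 hours and, with separate consent, followed until the child is one year old. That process starts only once someone knows of the pregnancy. For a leaver, the exit visit is the last planned occasion to find out.

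What is at stake is a small gain in safety follow-up for a few women. No estimate, comparison or dose-escalation rule is involved.

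**Working it through.** The plan gives no figure to reproduce. The check sets the two schedule columns side by side and then counts tests by time of exit.

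**Step 1. Day 84 against Early Termination.** Inputs: the Protocol 7.1 schedule, cross-checked against Sections 7.1.2, 7.1.3 and 7.2.6 and against SAP 10.2.

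| Row marked at Day 84 (safety and urine headings) | At Early Termination? |
|---|---|
| Clinical chemistry | yes |
| Haematology | yes |
| Fasting glucose | yes |
| ADA/nAb | yes |
| Urine pregnancy test | **no** |
| Vital signs | yes |
| 12-lead ECG | yes |
| Oxygen saturation | yes |
| Spirometry | yes |
| Diffusing capacity | yes |

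Total: 10 rows, of which 9 are repeated.

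This is my tally, not the protocol's, so I varied the counting rule:

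- Adding the physical examination (abbreviated at Day 84, full at exit) gives 10 of 11, with the pregnancy test still the only omission.
- Taking every row marked at Day 84 gives 13 of 17. The four missing are the pregnancy test, the restrictions check, the PK sample and TG2. The last three are not safety assessments.

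**Step 2. Is the blank cell an accident of the table?** No. Section 7.1.3 has no urine item, and Sections 7.1.2 and 7.2.6 both give the four days without naming early termination. Six investigation sections do name it: 7.2.2.4, 7.2.7.1, 7.2.7.2, 7.2.7.3, 7.2.8 and 7.2.9.

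**Step 3. Scheduled post-dose tests by time of exit.** The post-dose tests fall on Days 28, 56 and 84, so a completer has 3. The last column is the longest nominal time, ignoring visit windows, since the previous scheduled test.

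| Exit | Post-dose tests received | Longest time untested at exit |
|---|---|---|
| Before Day 28 | 0 of 3 | 28 − 1 = 27 days (since the pre-dose test) |
| After Day 28, before Day 56 | 1 of 3 | 56 − 28 = 28 days |
| After Day 56, before Day 84 | 2 of 3 | 84 − 56 = 28 days |
| Completer | 3 of 3 | tested at the final visit |

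**Step 4. How many women?** The documents give neither an expected number of women of childbearing potential nor a discontinuation rate, so the number affected cannot be calculated. The bounds are qualitative: 24 subjects plus replacements, all aged 40 or over, with IPF. The affected group is the women of childbearing potential among them who leave early and still attend an exit visit.

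**The case against.** The strongest reply is that this is a consistent design choice of little consequence.

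- **Classification.** Section 9.1 does not list pregnancy testing among the safety variables, and every 9.1 variable assessed at Day 84 is repeated at exit. That is correct. Against it, Section 7.2.6 is itself titled as urine collection for safety evaluation, so treating the test as a safety assessment is fair. A count of 9 of 10 should still not be presented as the protocol's own.
- **Consistency.** The protocol and the SAP agree in leaving the test out. A reader might infer an internal contradiction, but there is none.
- **The SAP as confirmation.** SAP 3.2.1 says "Serum and urine pregnancy test and FSH (at Screening, Day 1, Day 28, Day 56, and Day 84 only), will only be listed", which might be read as ruling out an exit test. It carries little weight. The same section also omits early termination for chemistry and haematology, which are scheduled there, and it attaches FSH to days on which the protocol does not measure it.
- **Other routes to discovery.** Adverse events are collected by spontaneous report, observation and open questioning (Section 10.8), and the exit visit includes a physical examination. Partner pregnancies are handled under Section 10.11 with no testing at all. This stands, and it lowers the stakes.
- **Interval.** The 27 or 28 days untested are no longer than the gaps completers have between tests. This is true, but a completer's gap always closes with a test and a leaver's does not.
- **Yield and reach.** A test within days of dosing detects little, and Section 4.4 excludes subjects who have withdrawn consent from the exit visit. Both points stand.

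A reader might also infer a gap in contraceptive cover, because inclusion criteria 11a(i) and 12a end the commitment at the last study visit without saying what that means for a leaver. The documents do not support that inference. Willingness is judged before enrolment, when the foreseeable last visit is Day 84, which Section 3 labels the end of study. On that reading there is no shortfall. Reading it as the last visit attended is possible, but nothing in the documents establishes it. The right duration would depend on half-life data held outside them, and the subject information is not available to check. At most this is a wording query.

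**Conclusion.** The point holds in a limited form. The urine pregnancy test is the one Day 84 safety assessment not repeated at Early Termination. A woman of childbearing potential who discontinues before Day 28 has 0 of 3 scheduled post-dose tests, and a later leaver has 1 or 2 of 3 and no closing test.

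This rests on reading the schedule and Sections 7.1.2, 7.1.3 and 7.2.6 together, on counting the pregnancy test as a safety assessment, and on the Day 1 test being pre-dose. It does not depend on how the last study visit is defined.

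Severity is low. Few women are likely to be affected, though the documents do not allow a number. The documents show no hazard, and no analysis or conclusion of the trial would change. It is worth raising because the remedy is cheap.

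**What to change.** Add a urine pregnancy test for women of childbearing potential to Section 7.1.3, to Section 7.2.6 and to the Early Termination column of the Section 7.1 schedule, and update the SAP 10.2 copy to match.

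The cost is one urine test, of a kind the study already uses on four days, for a few women at a visit they are already attending, plus short wording changes. No new output is needed, because SAP Listing 16.2.8.6 already takes all serum and urine pregnancy results and these results are only listed.

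Separately, as a wording query only, ask the sponsor to state whether the last study visit in inclusion criteria 11a(i) and 12a means the planned Day 84 visit for subjects who discontinue.
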